3.2.2.4 Supportive analyses

3.2.2.4.1 Analysis in a Bayesian framework

A secondary analysis will be conducted using a Bayesian approach with an informative prior distribution for the slope in the placebo arm. This informative prior distribution is based on natural history data collected during the National Tay-Sachs & Allied Diseases (NTSAD) annual conferences between 2015 and 2019. A summary of these data is provided in [Section 5.7](#).

In this secondary analysis, the linear mixed-effect model will be estimated in a Bayesian framework. An informative prior distribution for the slope of the placebo arm will be used, assuming the prior distribution of the slope of log-transformed 9-HPT has a normal distribution, with mean =0.0264 and standard deviation of 0.0118 (see [Table 25](#) for details). A non-informative prior distribution will be used for all other parameters of the linear mixed-effect model.

Efficacy of venglustat will be based on the posterior probability that the slope of annualized rate of change in 9-HPT on venglustat is lower than the slope on placebo. A posterior probability of at least 95% will be considered significant.

3.2.2.4.2 While-on-treatment analysis

A secondary analysis will target a while-on-treatment estimand.

In this sensitivity analysis, the linear mixed-effect model described in [Section 3.2.2.2](#) will be repeated, including only 9-HPT collected during the primary analysis period, up to the last IMP administration +30 days.

In case of presence of outlier, the linear mixed-effect model will be replaced by the robust ANCOVA on individual slopes, described in [Section 3.2.2.3.1](#). The exact criterion to detect outliers is presented in [Section 5.6.1.2](#).

3.2.2.4.3 Time to meaningful worsening in 9-HPT

A meaningful worsening in 9-HPT will be defined as an increase from baseline in 9-HPT, larger than or equal to a pre-defined threshold for meaningful worsening. The within-patient threshold for meaningful worsening will be determined from a psychometric analysis conducted on the blinded data with at least 75% of participants who completed the Week 104 assessments or withdrew from the EFC15299 study, that will be completed before the database lock.

In order to take into account within-participant fluctuations over time of the 9-HPT, a meaningful worsening in 9-HPT will be defined as an unresolved increase from baseline in 9-HPT. A meaningful worsening will therefore be defined as an increase from baseline in 9-HPT, larger or equal to the pre-defined threshold, that is observed at any visit (Week 12, 26, 52, 78 or 104), and is sustained at all subsequent visits until the Week 104 visit or study discontinuation (whichever comes first). In case an increase larger or equal to the pre-defined threshold is observed at the Week 104 visit (or at last visit in case of premature study discontinuation), the criterion for meaningful worsening will be considered met, since the worsening was not resolved during the study.

Time to meaningful worsening in 9-HPT will be defined as follows:

- For participants with meaningful worsening, time to meaningful worsening will be defined as the first visit (Week 12, 26, 52, 78 or 104) where an increase in 9-HPT larger or equal to the pre-defined threshold was observed, and not subsequently resolved.
- For participants without meaningful worsening, time to meaningful worsening will be censored at the last visit (Week 0, 12, 26, 52, 78 or 104) where 9-HPT was assessed.

An example of derivation of time to meaningful worsening and status is presented in [Table 5](#), with 4 hypothetical participants, and assuming for illustration purpose that the threshold for meaningful worsening is a $\geq 20\%$ increase in 9-HPT.

Table 5 - Examples of time to meaningful worsening in 9-HPT, assuming threshold for meaningful worsening is a $\geq 20\%$ increase from baseline

	Participant #1	Participant #2	Participant #3	Participant #4
Change from baseline in 9-HPT				
Week 12	+5%	+5%	+15%	+10%
Week 26	+25%	+25%	+5%	+25%
Week 52	+10%	+15%	+10%	Not done
Week 78	+25%	+25%	+15%	Not done
Week 104	+30%	+15%	+25%	Not done
Time to meaningful worsening				
Status	Event	Censor	Event	Event
Time to event/censor	78 weeks	104 weeks	104 weeks	26 weeks

Numbers in **bold** represent increase $\geq 20\%$.

Visits will be defined based on the analysis window defined in [Table 13](#).

Time to meaningful worsening in 9-HPT will be summarized graphically using Kaplan-Meier cumulative incidence curves. The proportion of participants with meaningful worsening at Week 104 will be obtained from the Kaplan-Meier estimates at Week 104 within each treatment arm. The proportion of participants with meaningful worsening at Week 104 will be informally compared between the two treatment arms, based on the SE of the Kaplan-Meier estimate using the Greenwood formula. Statistical test and (90%,95%) confidence intervals of the difference in proportion will be presented for descriptive purpose only, since not included in the procedure for handling multiplicity of tests.

In addition, in order to assess alternative thresholds for meaningful worsening, the same procedure will be repeated using different thresholds, varying from 5% increase to 100% increase in 9-HPT. Similar analysis will evaluate worsening based on absolute change from baseline, rather than relative change from baseline (with thresholds varying from 1 second increase to 60 seconds increase). The results will be presented in a cumulative graph, presenting the threshold for worsening on the X axis, and the proportion of participants with meaningful worsening at Week 104 (based on the threshold presented on the X axis) on the Y axis. The graph will present the proportions in the venglustat and placebo arm.

3.2.2.4.4 Time to meaningful improvement in 9-HPT

The same analysis will be conducted to evaluate meaningful improvement in 9-HPT.

A meaningful improvement in 9-HPT will be defined as decrease from baseline in 9-HPT, larger than or equal to a pre-defined threshold for meaningful improvement. The threshold for meaningful improvement will also be determined from the psychometric analysis. This analysis will be produced if such threshold is found with psychometric analysis.

A meaningful improvement will be defined as a decrease from baseline in 9-HPT, larger or equal to the pre-defined threshold, that is observed at any visit (Week 12, 26, 52, 78 or 104), and is sustained at all subsequent visits until the Week 104 visit. In case a decrease larger or equal to the pre-defined threshold is observed at the Week 104 visit, the criterion for meaningful improvement will be considered met. In case of missing data at Week 104, the criterion for meaningful improvement will not be considered met, even if a decrease in 9-HPT was observed at previous visits.

Time to meaningful improvement in 9-HPT will be defined as follows:

- For participants with meaningful improvement, time to meaningful improvement will be defined as the first visit (Week 12, 26, 52, 78 or 104) where a decrease in 9-HPT larger or equal to the pre-defined threshold was observed and maintained until Week 104.
- For participants without meaningful improvement, time to meaningful improvement will be censored at the last visit (Week 0, 12, 26, 52, 78 or 104) where 9-HPT was assessed.

An example of derivation of time to meaningful improvement and status is presented in [Table 6](#), with 4 hypothetical participants, and assuming for illustration purpose that the threshold for meaningful improvement is a $\geq 20\%$ decrease in 9-HPT.

Table 6 - Examples of time to meaningful improvement in 9-HPT, assuming threshold for meaningful improvement is a $\geq 20\%$ decrease from baseline

	Participant #1	Participant #2	Participant #3	Participant #4
Change from baseline in 9-HPT				
Week 12	-5%	-5%	-15%	-10%
Week 26	-25%	-25%	-5%	-25%
Week 52	-10%	-15%	-10%	Not done
Week 78	-25%	-25%	-15%	Not done
Week 104	-30%	-15%	-25%	Not done
Time to meaningful improvement				
Status	Event	Censor	Event	Censor
Time to event/censor	78 weeks	104 weeks	104 weeks	26 weeks

Numbers in **bold** represent decrease $\geq 20\%$

The analysis of time to meaningful improvement will be the same as for time to meaningful worsening.

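### Time to meaningful improvement: participants missing at Week 104 are ruled not improved yet censored early, so the Kaplan-Meier proportion matches neither the SAP's criterion nor the proportion had nobody been missing

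*SAP*

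**What the plan says.** SAP 3.2.2.4.4 makes an observed Week 104 value a condition for improvement: "In case of missing data at Week 104, the criterion for meaningful improvement will not be considered met", whatever was seen at earlier visits. For everyone who does not qualify, "time to meaningful improvement will be censored at the last visit (Week 0, 12, 26, 52, 78 or 104) where 9-HPT was assessed". Table 6 works this through: participant #4, with nothing recorded after Week 26, is censored at 26 weeks.

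On estimation, the section says only: "The analysis of time to meaningful improvement will be the same as for time to meaningful worsening". The worsening section, 3.2.2.4.3, takes the Week 104 proportion from Kaplan-Meier in each arm (it "will be obtained from the Kaplan-Meier estimates at Week 104 within each treatment arm") and compares the arms "based on the SE of the Kaplan-Meier estimate using the Greenwood formula". Tests and intervals "will be presented for descriptive purpose only, since not included in the procedure for handling multiplicity of tests".

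SAP 3.3.1.4 applies the method to 25FWT and FARS-neuro. The improvement analysis is produced only if the psychometric work yields a threshold.

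**The concern.** Kaplan-Meier treats a censored participant as someone whose outcome is unknown and who would have had events at the rate of those still followed. Here a participant without a Week 104 value has already been ruled a non-improver and can never be an event. Early censoring removes that person from later risk sets and so undoes the rule.

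A second effect works the other way. Someone who improves early and then leaves is in the risk set at the visit of improvement but is not counted as an event. Early event rates are therefore too low if the aim is the proportion with nobody missing.

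The Week 104 proportions, their 90% and 95% confidence intervals and, through the same-analysis sentence, the graphs over a range of thresholds would thus describe a quantity that the SAP does not define.

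**Working it through.** **Inputs.**
- Table 6, SAP 3.2.2.4.4: event 78 weeks; censored 104; event 104; censored 26.
- SAP 4: 38 venglustat, 19 placebo.
- SAP 5.6.3.3: placebo slope 0.0273 per year on the log scale; difference -0.0374, so venglustat slope 0.0273 - 0.0374 = -0.0101; slope SD 0.0192; within-subject SD 0.0791; exponential dropout reaching 10% at 2 years.
- Assumptions: improvement thresholds of 5%, 10% and 20% (the SAP has not set one), and 30% dropout as a stress case.

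**Step 1: reproduce the SAP.** Applying the written rules to the Table 6 data returns all four statuses and times exactly.

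**Step 2: Kaplan-Meier on Table 6.** The estimate is 1 - S, where S is the product of (1 - d/n) over event times, with d events among n at risk.
- Week 78: n = 3 (participant #4 left at Week 26), d = 1, factor 2/3.
- Week 104: n = 2, d = 1, factor 1/2.
- S = 2/3 x 1/2 = 1/3, so the reported proportion is 66.7%.
- By the SAP's criterion, 2 of 4 improved: 50.0%. The completers-only figure is 2/3 = 66.7%.

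With participant #4 censored at 104 weeks, S = 3/4 x 2/3 = 1/2, which gives 50.0%.

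**Step 3: contrast with worsening.** In Table 5 the same pattern for participant #4 is an event at Week 26. S = 3/4 x 2/3 x 1/2 = 1/4, so Kaplan-Meier gives 75%, equal to the crude 3/4. In the SAP's two examples the mismatch appears only for improvement.

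**Step 4: direction.** At each event time the risk set is no larger than if all non-improvers were kept to Week 104, and no smaller than the completers at risk. Kaplan-Meier therefore lies between events/N and events/completers. Take 38 participants, 10 improvers and 4 censored at Week 26:
- all events at Week 12: 10/38 = 26.3% by both methods;
- all events at Week 104: Kaplan-Meier 10/34 = 29.4% against 26.3%.

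The excess is strict only when someone is censored before a later event.

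**Step 5: trial scale, 10% dropout** (1000 simulated trials per setting; decimals kept so that the subtraction can be followed).

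| Threshold | Arm | Kaplan-Meier | By the rule | Excess (points) |
|---|---|---|---|---|
| 5% | venglustat | 38.64% | 35.68% | 2.96 |
| 5% | placebo | 17.50% | 16.15% | 1.35 |
| 10% | venglustat | 22.86% | 21.02% | 1.84 |
| 10% | placebo | 8.55% | 7.83% | 0.72 |
| 20% | venglustat | 4.39% | 3.98% | 0.41 |
| 20% | placebo | 1.04% | 0.95% | 0.09 |

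With no dropout the two methods agree. Kaplan-Meier was not below the rule in any simulated trial.

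**Step 6: behaviour as dropout rises** (venglustat, 10% threshold; a separate run, so values differ slightly from Step 5).

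| Dropout | Kaplan-Meier | By the rule | Gap (points) |
|---|---|---|---|
| 0% | 23.6% | 23.6% | 0 |
| 10% | 23.0% | 21.1% | 1.9 |
| 30% | 22.0% | 16.5% | 5.5 |

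The gap widens because the rule-based proportion falls quickly, while Kaplan-Meier falls slowly. At 30% dropout the completers-only proportion is 23.6%, which recovers the no-dropout value in this model. Kaplan-Meier, at 22.0%, does not.

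**The case against.** The best defence is that the rules do not collide. One sets event status, the other sets the time for non-events, and Table 6 applies both without ambiguity. Nowhere does the SAP define the reported proportion as events/N, so preferring that figure could be called a choice of estimand. This stands in part: the instructions can be executed as written. It fails as a full answer because the result estimates neither natural target (Steps 2 and 6), and the SAP names no third one.

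The defence also points out that events/N is more sensitive to dropout than Kaplan-Meier, and that is correct. In Step 6, two arms with the same underlying improvement but 10% and 30% dropout would differ by 23.0 - 22.0 = 1.0 point under Kaplan-Meier and by 21.1 - 16.5 = 4.6 points under the rule. This is a real cost of the rule that the SAP chose, and the reader of the table needs to see it.

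A reader might go further and infer that the Kaplan-Meier figure rises with dropout, so that the arm losing more participants is credited with more improvement. The documents do not support this. Under the SAP's own simulation inputs the Kaplan-Meier value falls slightly as dropout rises. An example can show a rise if it adds dropouts while holding the number of improvers fixed, but that assumes that nobody who would have improved leaves.

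**Conclusion.** The point holds as a mismatch between the improvement criterion and its estimator. The reported Week 104 proportion is equal to or higher than the proportion meeting the SAP's criterion and, under the SAP's simulation model, somewhat lower than the proportion with nobody missing.

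The size is 66.7% against 50.0% in Table 6. At trial scale with 10% dropout and thresholds of 5% to 10%, it is about 2 to 3 points on venglustat and about 1 on placebo, and less at a 20% threshold. These trial-scale figures rest on the SAP's slopes, variances and outcome-independent dropout, and on assumed thresholds.

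The consequence is limited. The analysis is supportive, lies outside the multiplicity procedure and depends on a threshold being found. It does not touch the co-primary conclusion, and it gives no ground for expecting a bias in favour of either arm.

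**What to change.** Keep the missing-equals-not-improved rule and, in SAP 3.2.2.4.4, set the censoring time of every participant without meaningful improvement to Week 104. The Table 6 entry for participant #4 becomes censored at 104 weeks. The curve then ends at events/N, and the Greenwood variance reduces to p(1 - p)/N. Reporting the simple proportion with that standard error is equivalent at Week 104. Apply the change to 25FWT and FARS-neuro through 3.3.1.4, and leave the worsening analysis as it is.

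Because this figure falls as dropout rises, show it next to the counts of participants who did not complete the assessment, by arm and visit, already planned in 3.2.2.4.5. If the sponsor wants the proportion had nobody been missing, the SAP should say so and replace the rule, because the present method does not deliver that either.

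The cost is one SAP sentence and one table entry. No new data are needed, and the primary analysis does not change.

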3.2.2.4.5 Descriptive analysis by visit

Results will be summarized using descriptive statistics at each time point, including values, change and percent change from baseline.

Two graphs will be produced: one presenting the mean value \pm SE by visit, the other presenting the mean change from baseline \pm SE by visit.

Number and percentages of participants who did not complete the assessment will be described by time point.

3.2.3 Subgroup analyses

To assess the homogeneity of the treatment effect across various subgroups, analyses will be performed on the two co-primary endpoints across subgroups. Subgroup analyses will include, but not be limited to the following subgroups:

- Sex (Male, Female).
- Age group (<35, \geq 35 years).
- Disease type (Tay-Sach disease versus Sandhoff disease).
- Time from diagnosis (<5 years, \geq 5 years).
- Time from symptom onset (<20 years, \geq 20 years).
- Age at diagnosis (<30 years, \geq 30 years).
- Ability to walk (yes versus no).
- Baseline GM2 level (<median value, \geq median value).
- Baseline 9-HPT (<30 sec, \geq 30 sec).
- Baseline 25-FWT (<10 sec, \geq 10 sec or unable to walk).
- Baseline FARS-neuro (<50, \geq 50).

Treatment-by-subgroup interaction term and the subgroup factor term will be added in the primary model.

The treatment effects (venglustat versus placebo) for the primary endpoint will be provided, as well as the corresponding 90% and 95% CI, for each subgroup, using the same method as applied to the primary analysis. Forest plots will be provided.

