The 25FWT is a quantitative mobility and leg function performance test based on a timed 25-foot walk. The patient is directed to one end of a clearly marked 25-foot course and is instructed to walk 25 feet as quickly as possible, but safely. The time is calculated from the initiation of the instruction to start and ends when the patient has reached the 25-foot mark. The task is immediately administered again by having the patient walk back the same distance. Patients may use assistive devices when doing this task. Administration time will vary depending upon the ability of the patient. Total administration time should be approximately 1 to 5 minutes. The score for the 25FWT is the average of the 2 completed trials. The 25FWT will be administered in patients able to walk at baseline. Patients who cannot walk even with assistance will not be assessed. Since approximately 21% of patients who participated in the NTSAD study were wheelchair bound, it is expected that 25FWT will not be ascertained in a substantial fraction of the study population. For this reason, the 25FWT will not be considered as the primary endpoint in this study but will be included as a supportive secondary endpoint.

The FARS includes a neurological examination that specifically reflects neural substrates affected in Friedreich ataxia. The FARS-neuro is a performance outcome (PerfO), composed of 4 sections that assess different neurological faculties: bulbar activity (4 items), upper limb coordination (5 items), lower limb coordination (2 items), peripheral nervous system (5 items) and upright stability (7 items). The total score ranges from 0 to 117. The neurological examination domain of FARS is conducted by the clinician and has shown sensitivity to change overtime in a Sanofi natural history study. Based on the study findings, FARS neuro could be used to assess the different neurological signs in patients with GM2 gangliosidosis. To avoid dilution of this small effect in this slowly progressive disease, the Sponsor proposes studying the change in the neurological component of the FARS as an individual secondary endpoint.

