3 STATISTICAL ANALYSES

3.1 GENERAL CONSIDERATIONS

Statistical significance for comparison between venglustat and placebo will be assessed at the Type I error rate of 0.05 one sided. Although a typical criterion for concluding that a trial is positive is a p-value of <0.05 two-sided, a higher Type I error rate of 0.05 one-sided was selected due to the rarity of late-onset GM2 gangliosidosis, the seriousness of this disease and lack of available therapy, as per Food and Drug Administration (FDA) draft guidance (1).

In general, continuous data will be summarized using the number of observations available, mean, standard deviation (SD), median, [Q1, Q3] minimum, and maximum. Categorical and ordinal data will be summarized using the count and percentage of participants.

The baseline value is defined as the last available value before or equal to the first dose of investigational medicinal product (IMP) date in the primary analysis period. For participants randomized but not exposed, the baseline value is defined as the last available value before or equal to the date of randomization.

Unless otherwise specified, analyses will be performed by intervention group (and overall for baseline and demographics characteristics).

The two analysis periods described below are defined:

- The **primary analysis period** is defined as the period starting at the date of signed informed consent, and ending at the end of Week 104 visit, or the day before the first IMP OLE administration (whichever comes last). For participants not exposed to IMP in the OLE, the primary analysis period ends at the date of end of study.
- The **OLE period** (only for participants exposed to IMP in the OLE) is defined as the period starting the day after the end of primary analysis period, until the end of the study.

Within each analysis period, the following observation periods are defined:

During the **primary analysis period** (as defined above), the following observation periods are defined:

- The **pre-treatment period** is defined as the time from the signed informed consent date up to the first IMP administration.
- The **treatment-emergent (TE) period** is defined as the time from the first IMP administration to the last administration of IMP during the primary analysis period +6 weeks (including any temporary treatment discontinuation period, if any) or the end of the primary analysis period (whichever comes first).

The TE period includes the following 2 periods:

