The second co-primary endpoint in the primary population is the annualized rate of change in 9-HPT from baseline to Week 104.

3.2.2.2 *Main analytical approach*

[figure not shown]
The primary analysis will include all data collected in patients from the primary population, regardless of whether or not participants completed the treatment period. Patients who prematurely and permanently discontinue study medication will be requested to continue to be assessed after treatment discontinuation, up to the Week 104 visit. Data collected after treatment discontinuation will be included in the primary analysis. All efforts will be made to minimize the amount of missing data.

The 9-HPT will be derived from the two trials for each hand (see [Section 5.5.1](#) for derivation of the 9-HPT).

Annualized rate of change in 9-HPT will be compared between venglustat and placebo using a linear mixed-effect model.

The model will assume linear change over time in 9-HPT after log transformation. The logarithm transformation was selected due to anticipated non-normal distribution of the 9-HPT. Analysis of natural history data showed that logarithm transformation improved the normality of the distribution and reduced the impact of outliers (see [Figure 1](#)). A logarithm transformation will allow interpretation in terms of relative increase in time to complete the 9-HPT (annual % increase per year).

Figure 1 - Distribution and QQ-plot of Studentized residuals from the linear mixed-effect model on natural history data - With or without log transformation

The model will include separate slopes for the venglustat and placebo arm. In addition, the model will include random intercept and slope in order to account for the between subjects variability. A residual variance will account for the within-subject variability.

The linear mixed-effect model is based on the following equation:

$$y_{ijk} = \alpha_j + \beta_j t_{ijk} + u_{1ij} + u_{2ij} t_{ijk} + \varepsilon_{ijk}$$

Where:

- y_{ijk} is the log-transformed 9-HPT of subject i from group j at the k^{th} assessment.
- t_{ijk} is the time (in years) from randomization of the k^{th} assessment of 9-HPT.
- α_j is the fixed intercept of group j .
- β_j is the fixed slope of group j .
- u_{1ij} and u_{2ij} are the random intercept and random slope of subject i from group j .
- ε_{ijk} is the residual error.

The linear mixed-effect model makes the following assumptions:

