$$\begin{pmatrix} u_{1ij} \\ u_{2ij} \end{pmatrix} \sim N\left(\begin{pmatrix} 0 \\ 0 \end{pmatrix}, \begin{pmatrix} \sigma_I^2 & \rho\sigma_I\sigma_S \\ \rho\sigma_I\sigma_S & \sigma_S^2 \end{pmatrix}\right)$$

$$\varepsilon_{ijk} \sim N(0, \sigma_R^2)$$

$$\begin{pmatrix} u_{1ij} \\ u_{2ij} \end{pmatrix} \text{ and } \varepsilon_{ijk} \text{ are independent}$$

Where:

- σ_I^2 is the variance of random intercepts.
- σ_S^2 is the variance of random slopes.
- σ_R^2 is the variance of residual errors.
- ρ is the correlation between random intercepts and random slopes.

For the primary analysis, the linear mixed-effect model will be estimated in a Frequentist framework.

This model will provide mean estimate of the slope of log-transformed 9-HPT with their corresponding SE. A back-transformation (ie, exponential transformation) will be applied to obtain annualized rate of change of 9-HPT (in % per year) within each treatment arm:

$$\text{Annualized rate of change (\%/year)} = [\exp(\text{mean slope of log-transformed 9-HPT}) - 1] \times 100$$

The difference in annualized rate of change will be used to compare the venglustat group to the placebo group. The difference in LS means will be presented with its associated 90% confidence interval (see [Section 5.6.2](#)) and one-sided p-value. Statistical significance will be assessed at the one-sided 0.05 level (see [Section 3.1](#) for justification).

In case the results from the linear mixed-effect model may be severely impacted by the presence of outliers (participants with extremely low or extremely high slope of log-transformed 9-HPT), the linear mixed-effect model will be replaced by the robust ANCOVA on individual slopes, described in [Section 3.2.2.3.1](#). The exact criterion to determine whether the robust ANCOVA should be used is presented in [Section 5.6.1.2](#).

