3.3.1.2.2 Change in 25FWT

The 25FWT will be derived from the two trials (see [Section 5.5.2](#) for derivation of the 25FWT).

Change in 25FWT will be analyzed only in participants able to walk at baseline. Participants unable to complete the 25FWT at baseline will be excluded from this analysis. To ensure balanced randomization of subjects able to walk at baseline, the randomization will be stratified based on the participant's ability to walk at the baseline visit.

Change in 25FWT will be compared between venglustat and placebo using a linear mixed-effect model with random intercept and slopes, similar to the analysis of the 9-HPT (see [Section 3.2.2.2](#)). The model will assume linear change over time in 25FWT after log transformation. The logarithm transformation was selected due to anticipated non-normal distribution of the 25FWT. A logarithm transformation will allow interpretation in terms of relative increase in time to complete the 25FWT (annual % increase per year).

Slope on venglustat and on placebo will be estimated from the linear mixed effect model. Efficacy of venglustat will be based on the comparison of slopes. The difference in slopes will be estimated and presented with its associated 90% confidence interval and p-value. Significance level will be the same as for the primary endpoint.

In case of outliers, the linear mixed-effect model will be replaced by the robust ANCOVA on individual slopes, described in [Section 3.2.2.3.1](#). The exact criterion to determine whether the robust ANCOVA should be used is presented in [Section 5.6.1.2](#).

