3.3.1.5 Subgroup analyses

The subgroup analyses described in [Section 3.2.3](#) will also be conducted for the three secondary endpoints presented above.

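### For 9-HPT, 25FWT and FARS-neuro, the subgroup terms added to the mixed model change intercepts only, so the model cannot give a slope difference per subgroup

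*SAP*

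**What the plan says.** SAP 3.2.3 covers both co-primary endpoints with a single modelling instruction: "Treatment-by-subgroup interaction term and the subgroup factor term will be added in the primary model". The next sentence says that treatment effects will be given "as well as the corresponding 90% and 95% CI, for each subgroup, using the same method as applied to the primary analysis", with forest plots. The section lists 11 subgroup factors. SAP 3.3.1.5 states that the same analyses "will also be conducted for the three secondary endpoints presented above".

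For 9-HPT, the model in SAP 3.2.2.2 has a fixed intercept and a fixed slope for each arm, plus a random intercept and slope: "The model will include separate slopes for the venglustat and placebo arm". The effect measure follows from that: "The difference in annualized rate of change will be used to compare the venglustat group to the placebo group". The program in SAP 5.6.3.3 agrees: its fixed effects are group, time and group*time, and the estimated contrast is group*time. SAP 3.3.1.2.2 and 3.3.1.2.3 use the same kind of slope model for 25FWT and FARS-neuro.

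No section of either document gives a subgroup-by-time or treatment-by-time-by-subgroup term.

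**The concern.** The two terms suit a model in which the treatment effect is a main effect, such as the CSF GM2 ANCOVA. In a slope model the effect lies in treatment-by-time. A subgroup term and a treatment-by-subgroup term without time move the level of the curves and leave one slope difference for everyone. The interaction coefficient then describes a constant difference in level between arms, not whether the effect on progression differs between subgroups, which is the stated purpose of SAP 3.2.3.

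Followed literally, the forest plot would show a homogeneous effect whatever the data contained, with intervals too narrow for every subgroup. To produce what was promised, the programmer would have to depart from the SAP and could make that choice after unblinding.

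**Working it through.** **Inputs.** These come from the program in SAP 5.6.3.3: 38 and 19 participants; visits at 0, 0.25, 0.5, 1, 1.5 and 2 years; SD of intercept 0.4841, of slope 0.0192 and of residual 0.0791, with intercept and slope independent; 10% exponential dropout by 2 years; assumed slope difference -0.0374 per year on the log scale. The test level is one-sided 0.05 (SAP 3.1).

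**The plan's own figure first.** SAP section 4 states about 80% power for 9-HPT. The centred sum of squares of the visit times is 2.96875, so without dropout the SD of an individual slope is sqrt(0.0192² + 0.0791²/2.96875) = 0.0498. The SE of the slope difference is 0.0498 × sqrt(1/38 + 1/19) = 0.0140, which gives 84.9% power. With the number of participants multiplied by 0.9, power is 81.4%. Simulating from the SAP's data-generating code with REML fits (1013 runs) gave 81.6%. The stated power is reproduced, so the inputs can be relied on.

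**Structure.** Let g be arm, t time and s subgroup (0 or 1). Under the rule as written:

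E[y] = a + b·g + c·t + d·g·t + e·s + f·g·s

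The slope difference between arms is d for s = 0 and d for s = 1. The coefficients e and f never multiply t. Adding h·s·t + k·g·s·t makes the slope difference d for s = 0 and d + k for s = 1.

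**Precision.** These figures come from the information matrix of the generalized least squares fit with the inputs above, including dropout. The half-width is 1.645 × SE.

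| Model and split | SE of slope difference | 90% half-width |
|---|---|---|
| Rule as written, either split | 0.0146 for both subgroups | 0.024 |
| With time terms, 50:50 | 0.0206 and 0.0206 | 0.034 and 0.034 |
| With time terms, 79:21 (30+15 and 8+4) | 0.0164 and 0.0318 | 0.027 and 0.052 |

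These agree with simple scaling of the overall SE: 0.0146 × sqrt(2) = 0.0206; 0.0146 × sqrt(57/45) = 0.0164; 0.0146 × sqrt(57/12) = 0.0318.

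The 50:50 split is an assumption. The 79:21 split applies to ability to walk and assumes the natural-history share in Protocol 3.1, where "approximately 21% of patients who participated in the NTSAD study were wheelchair bound".

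**Bias.** Suppose the true slope differences are 0 and -0.0374 in two equal halves. The rule as written estimates their average for both: (0 - 0.0374)/2 = -0.019. The model with time terms returns 0 and -0.037.

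**Check on simulated data.** With true differences of 0 and -0.0748 in two halves (500 trials), the rule as written gave -0.0378 for both, equal to the model with no subgroup terms to five decimals. The full model gave -0.0004 and -0.0754. In one trial fitted by REML, the slope difference was -0.0268 (SE 0.0190) both without subgroup terms and under the rule as written. The full model gave +0.0124 and -0.0719. On the same data, the robust ANCOVA on individual slopes with only the two terms gave distinct effects, +0.025 and -0.065.

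**What the fix cannot supply.** The SE of the difference between subgroups is sqrt(0.0206² + 0.0206²) = 0.029 at 50:50 and sqrt(0.0164² + 0.0318²) = 0.036 at 79:21. An interaction as large as the whole assumed effect is then 0.0374/0.029 = 1.3 or 0.0374/0.036 = 1.0 SE, with power of 36% and 27% at one-sided 0.05. Without dropout these SEs are 0.0280 and 0.0343.

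**The case against.** The best defence is that the sentence is shorthand. SAP 3.2.3 aims at homogeneity of the treatment effect and asks for effects by the same method as the primary analysis. For 9-HPT that is a slope difference, so treatment-by-subgroup could mean treatment-by-time-by-subgroup. Alternatively, the phrase about the same method could mean refitting the model within each subgroup. Either would deliver the promised output, and a forest plot with identical rows would probably be noticed. The analyses are also descriptive, lie outside the multiplicity procedure and have low power.

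Part of this stands. The intent is probably a slope difference per subgroup, nothing confirmatory depends on it, and the low precision comes from splitting 57 participants, not from this wording. But neither alternative reading is written in the SAP. Refitting conflicts with the sentence that adds interaction terms to one model, and it would re-estimate variance components in groups as small as 8 and 4. That several readings are possible is itself a reason to settle the text before unblinding.

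The robust ANCOVA does work with two terms, but it replaces the mixed model only if the outlier criterion is met. The mixed model is the default.

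**Conclusion.** The concern holds for the linear mixed-effect models of 9-HPT, 25FWT and FARS-neuro. As written, the rule gives one slope difference for all subgroups and cannot give the subgroup-specific effects and intervals promised in the next sentence. That slope difference does not depend on the variance inputs or on the split: it follows from the model equation.

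The sizes do depend on assumptions: the SAP's simulation variances for 9-HPT, 10% dropout and the two illustrative splits. Under these, the reported half-width would be 0.024 instead of 0.034 at 50:50. At 79:21 it would be 0.024 instead of 0.052 in the smaller subgroup, less than half the proper width. The pattern of 0 and -0.0374 is an illustration and is not taken from the documents.

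The two-term rule is adequate for percent and absolute change in CSF GM2 and for the robust ANCOVA. The change should be made, but it does not touch the primary conclusion.

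**What to change.** Amend SAP 3.2.3 before unblinding to state, for the linear mixed-effect slope models:

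- The added terms are subgroup, subgroup-by-time, treatment-by-subgroup and treatment-by-subgroup-by-time.
- The effect in each subgroup is its own difference in slopes (treatment-by-time plus the three-way term where it applies), with its 90% and 95% intervals. For 9-HPT, the back-transformation in SAP 5.6.2 is applied to the subgroup-specific slopes.
- Any interaction test that is reported uses the three-way term.

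Keep the two-term rule for the CSF GM2 ANCOVAs and the robust ANCOVA on individual slopes. Add that ability to walk is not a subgroup for 25FWT, because "Change in 25FWT will be analyzed only in participants able to walk at baseline", and that subgroup estimates are descriptive with low precision.

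The cost is one or two sentences for the model and two more model terms. No new data are needed, and the primary analysis and sample size do not change.
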